9.1 Adverse Events

An adverse event is defined as any untoward medical occurrence in a clinical investigation patient administered a pharmaceutical product, which does not necessarily have a causal relationship with this treatment. An adverse event can therefore be any unfavorable and/or unintended sign (including an abnormal laboratory finding), symptom, or disease temporally associated with the use of an investigational medicinal product, whether or not related to the investigational medicinal product. All adverse events, including observed or volunteered problems, complaints, or symptoms, are to be recorded on the appropriate eCRF.

Adverse events, which include clinical laboratory test variables, will be monitored and documented from the time of informed consent until the EOS Visit. Patients should be instructed to report any adverse event that they experience to the Investigator, whether or not they think the event is due to study drug. Beginning at the time of informed consent, Investigators should make an assessment for adverse events and record the event on the appropriate adverse event eCRF. Beginning with receipt of first dose of study drug, any adverse event that occurs during the Treatment Period will be recorded as a TEAE on the appropriate eCRF.

Wherever possible, a specific disease or syndrome rather than individual associated signs and symptoms should be identified by the Investigator and recorded on the eCRF. However, if an observed or reported sign or symptom is not considered a component of a specific disease or syndrome by the Investigator, it should be recorded as a separate adverse event on the eCRF. Additionally, the condition that led to a medical or surgical procedure (eg, surgery, endoscopy, tooth extraction, or transfusion) should be recorded as an adverse event, not the procedure itself.

Any medical condition already present at screening should be recorded as medical history and not be reported as an adverse event unless the medical condition or signs or symptoms present at baseline changes in severity, frequency, or seriousness at any time during the study. In this case, it should be reported as an adverse event: worsening of preexisting condition.

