9.12.1 Pruritus Management – Guidance to Investigators

Mostly mild to moderate pruritus has been observed in clinical trials with EYP001a and has also been reported with other FXR agonists and in patients with NASH. Pruritus is also part of the natural disease symptomatology of NASH and independent of any pharmacological treatment. Tolerance to pruritus may develop over continuous, uninterrupted dosing or after a short (few days) interruption of EYP001a (empirical observations).

The following 3-level therapeutic approach to pruritus should be applied:

1. Topical non-pharmacological or over-the-counter interventions to improve pruritus may be tried and can be advised to patients. These include application of moisturizers, cooling agents, and antihistamines; or taking cool showers/showering in the morning, using clear/gentle soaps and laundry detergents, application of cold packs or fabric strips soaked in cold water, avoidance of wool or other irritating fabrics, and wearing loose-fitting clothing.
2. In the case of no improvement of pruritus, a drug holiday of 2 days to a maximum of 5 days may be implemented.
3. In the case pruritus prevails and requires systemic oral pharmacological treatment, it is encouraged to seek advice from the Medical Monitor. Recommended possible comedications for pruritus are: naltrexone (25 to 50 mg/day orally [po]), ondansetron (4 to 24 mg/day po), hydroxyzine (25 to 75 mg/day po), sertraline (25 to 75 mg/day po), and gabapentin 300 mg/day po).

Note: Bile acid sequestrants are excluded medications, the concomitant use of naltrexone with gabapentin is disallowed.

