10.2.4.1 Adverse events

The original terms used in the eCRF by Investigators to identify adverse events will be coded using the current version of the Medical Dictionary for Regulatory Activities (MedDRA). All adverse events will be assessed and reported using the National Cancer Institute CTCAE Version 5.0 grading system. A TEAE is defined as a new or worsening adverse event after the first dose of study drug. The percentage of patients with TEAEs will be summarized for each dose group by system organ class and preferred term. The study drug-related TEAEs and SAEs will be summarized in the same fashion. The TEAEs will also be summarized by system organ class, preferred term, and maximum severity. All SAEs and TEAEs leading to early discontinuation will be listed.

The safety of EYP001a with statin coadministration will be assessed based on the difference in frequency of TEAEs between treatment groups.

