Table 8. Schedule of Procedures – Part B

	Screening ^a	Treatment Period								EOS FUP Visit	ET Visit ^b
		0	2	4	6	8	10	12	14		
Study Week	-12 to -1	Day 1	Day 14	Day 28	Day 42	Day 56	Day 70	Day 84	Day 98		
Study Day ^b	-84 to -3										
Assessment											
Informed consent	X										
Eligibility criteria	X	X ^b									
Demographics	X										
Medical history	X ^b										
Prior/concomitant medications ^b	X	X	X	X	X	X	X	X	X	X	
Height and body weight ^b	X	X	X	X		X		X	X	X	
BMI calculation ^b	X	X	X	X		X		X	X	X	
Waist and hip circumference ^b	X	X	X	X		X		X	X	X	
WHR and WHtR calculations ^b	X	X	X	X		X		X	X	X	
Physical examination ^b	X	X	X	X		X		X	X	X	
Vital signs ^b	X	X	X	X		X		X	X	X	
AUDIT-C ^b	X			X		X		X		X	
Randomization ^b		X									
Adverse event monitoring ^c	X	X	X	X	X	X	X	X	X	X	
Viral serology ^b	X										
Chemistry, hematology, and coagulation ^b	X	X	X	X	X ^b	X	X ^p	X	X	X	
Lipid and metabolic profile ^c	X	X	X	X		X		X	X	X	
Urinalysis ^b	X	X	X	X		X		X	X	X	
Pregnancy test ^b	X	X	X	X		X		X	X	X	
12-Lead ECG ^b	X		X	X		X		X	X	X	
FibroScan ^b	X							X		X	
MRI-PDFF and cT1 imaging ^b	X							X		X ^b	
Diet/lifestyle counseling ^b	X	X	X	X		X		X	X	X	
PD biomarker sampling ^b		X	X	X		X		X	X	X ^b	
Liver fibrosis and inflammation sampling ^b			X		X		X			X	X
PK sampling ^b		X	X	X		X		X	X	X ^y	

Table 8. Schedule of Procedures – Part B (Continued)

	Screening ^a	Treatment Period								EOS FUP Visit	ET Visit ^c
		-12 to -1	0	2	4	6	8	10	12	14	
Study Week	-84 to -3	Day 1	Day 14	Day 28	Day 42	Day 56	Day 70	Day 84	Day 98		
Assessment											
Blood sampling for plasma storage ^b	X	X	X	X		X		X	X	X	X
Dispense EYP001a or placebo		X	X	X	X	X	X	X			
Collect used/unused study drug and assess compliance			X ^{cc}	X ^{cc}	X	X ^{cc}	X ^{cc}	X ^{cc}		X	
Blood sample collection will be prioritized starting with the safety sample. All blood samples should be collected while the patient is in a fasted state, defined as nothing by mouth except water for ≥6 hours.											
a.	The Screening Period may be up to 12 weeks in duration. A patient who is first designated as a screen failure prior to being randomized may be rescreened upon Sponsor or designee approval. If the patient was screen failed after the MRI-PDFF was completed, the original MRI-PDFF scan may be utilized for rescreening, provided it was obtained within 1 month prior to rescreening.										
b.	A ±3-day window is acceptable for all visits during the Treatment Period.										

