3.7.1 Adverse Events (AEs)

An AE is defined as any untoward medical occurrence in a clinical investigation patient administered a pharmaceutical product, which does not necessarily have a causal relationship with this treatment. An AE can therefore be any unfavorable and/or unintended sign (including an abnormal laboratory finding), symptom, or disease temporally associated with the use of an investigational medicinal product, whether or not related to the investigational medicinal product.

For analysis, a treatment emergent AE (TEAE) is defined as a new or worsening AE after the first dose of study drug. Programmatically, this will be identified as any AE with a start date on or after the date of first dose. If part of the date for the onset/end of an AE is missing, but the existing parts allow determination of timing of AE onset relative to the first dose of study drug, then the AE will be classified as treatment-emergent or not per review of the existing parts of the date. If timing of the AE onset/end relative to the first dose of study drug cannot be determined, then the AE will be assumed to be treatment-emergent.

A summary overview of all AEs will be provided, which presents the number and percentage of patients in each treatment group from the Safety Population, including number of events, satisfying each of the following categories:

- Any AE
- Any TEAE
- Maximum severity of TEAEs
- Study drug-related TEAEs
- Maximum severity of study drug-related TEAEs
- TEAEs of special interest:
 - Part A: pruritus, Drug Induced Liver Injury (DILI) and muscle-related

➤ Part B: elevation of transaminases and muscle-related

- All serious AEs (SAEs)
- All serious TEAEs (TESAEs)
- All study drug-related TESAEs
- TEAEs leading to early discontinuation
- TEAEs leading to temporary discontinuation of study drug
- TEAEs leading to dose reduction

AEs will be coded using MedDRA v22. The number and percentage of patients with AEs, including the number of AEs, will be summarized by their MedDRA preferred term within system organ class and treatment group. For patient count summaries, multiple AE events with the same MedDRA coded terms (preferred term and system organ class) from the same patients will only be counted once. Similar summaries will be presented for study drug-related TEAEs and TESAEs.

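### The SAP's programming rule for treatment-emergent AEs tests only the start date, so it drops the worsening half of its own definition

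*SAP*

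**What the plan says.** Two consecutive sentences of SAP 3.7.1 set the rule. The first is the definition: "a treatment emergent AE (TEAE) is defined as a new or worsening AE after the first dose of study drug". The second is its implementation: "Programmatically, this will be identified as any AE with a start date on or after the date of first dose". The rest of that paragraph deals only with partial or unknown dates. If timing relative to the first dose cannot be worked out, "then the AE will be assumed to be treatment-emergent".

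Protocol 10.2.4.1 has the same definition and no programming rule: "A TEAE is defined as a new or worsening adverse event after the first dose of study drug". SAP Section 5, which lists departures from the protocol's analyses, does not mention a date-only rule.

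On collection, Protocol 9.1 says that AEs "will be monitored and documented from the time of informed consent until the EOS Visit". In Appendix A, "The Screening Period may be up to 12 weeks in duration". AEs with a start date before dosing will therefore be in the database.

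On conditions that patients bring with them, Protocol 9.1 says: "Any medical condition already present at screening should be recorded as medical history". It makes an exception when the condition, or signs or symptoms present at baseline, change in severity, frequency or seriousness during the study. That change is then reported as an AE of worsening. The same section asks for significant worsening of laboratory or ECG findings present at screening to be reported as AEs.

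**The concern.** The definition has two limbs, new and worsening, and the program implements only the first. If an AE starts during screening and its grade rises on drug within one record, its start date stays before the first dose. The definition calls it treatment-emergent; the program does not.

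The TEAE tables carry the main safety comparison. Protocol 10.2.4.1 also bases the statin-coadministration objective on the difference in TEAE frequency between groups. Pruritus is the symptom of most interest, and onset before dosing is plausible, because Protocol 9.12.1 states: "Pruritus is also part of the natural disease symptomatology of NASH and independent of any pharmacological treatment". If the drug aggravates existing symptoms more than placebo does, the omitted events would come mostly from the active arms, and the TEAE contrast would be understated for those events.

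**Working it through.** No published figure is at issue, so the check applies the definition and the rule to the same cases. Day numbers follow SAP 3.1.2, where the calendar day of first dose is Day 1. The rule is: TEAE if start date ≥ date of first dose. The day and grade values are illustrations.

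| Case | Definition | Rule | Agree? |
|---|---|---|---|
| 1. New AE, onset Day 10 | TEAE | Day 10 ≥ Day 1: TEAE | Yes |
| 2. AE starts and resolves in screening | Not TEAE | Start < Day 1: not TEAE | Yes |
| 3. Itch starts Day -20 at Grade 1, reaches Grade 3 on Day 30, one record | TEAE (worsening) | Day -20 < Day 1: not TEAE | **No** |
| 4. As case 3, but the worsening has its own record dated Day 30 | TEAE | Day 30 ≥ Day 1: TEAE | Yes |
| 5. AE on Day 1 before the first tablet | Not TEAE | Day 1 ≥ Day 1: TEAE | No, but conservative |

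Cases 3 and 4 differ only in how the site records the worsening. Whether the rule works therefore depends on a recording convention, and the next step is to see whether the documents supply one.

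- Protocol 9.1 requires a worsening AE for conditions otherwise held as medical history, or signs present at baseline. It does not state the onset date of that record.
- It does not say that an AE already on the AE form since consent gets a second record when it worsens.
- It says that an AE occurring in the Treatment Period after the first dose is recorded as a TEAE. That does not settle what happens to an AE that began earlier and is continuing.
- SAP 3.7.1 is silent on the matter.

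Next, what case 3 loses and keeps under SAP 3.7.1 to 3.7.3:

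- Lost: the rows for any TEAE, maximum severity, drug-related TEAEs, TEAEs of special interest, serious TEAEs, and TEAEs leading to discontinuation, interruption or dose reduction, with the separate listings for those last three; the statin and non-statin TEAE tables; and the derived pruritus TEAE summary.
- Kept: the any-AE row, the all-SAE row, the AE table by preferred term and system organ class, and the listings of all AEs, AEs of special interest and SAEs.
- Independent backstop: ALT, AST and total bilirubin have tables of baseline against maximum post-baseline grade. Part A itch scales are summarized as change from baseline. Part B itch scales are given only if itch is reported and are only listed, so Part B pruritus has no such backstop.

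On scale, the planned Part B arm is 30 patients, so one patient missing from a row moves that arm by 1/30 = 3.3 percentage points. That holds only if the patient has no other TEAE that qualifies for the same row. The documents give nothing from which to estimate how many such patients there would be.

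**The case against.** The strongest reply is that Protocol 9.1 already handles case 3. Its trigger includes signs or symptoms present at baseline, and Protocol 10.2.4 sets the safety baseline as the last evaluation before the first dose. On that reading, Grade 1 itch on Day 1 that reaches Grade 3 is reported as a worsening AE. If that record is dated at the worsening, the start-date rule captures it. Long-standing itch from NASH would often predate screening and fall squarely under this instruction. Record handling may also be set out in eCRF guidance or in the separate programming specifications that SAP Section 6 mentions.

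Much of this stands, and it narrows the gap to AEs that begin between consent and Day 1, persist, worsen on drug and stay on one record. It does not close the gap. The Protocol 9.1 sentence concerns conditions otherwise entered as medical history, gives no onset date, and does not say that an existing AE record is split. A start-date rule is sound only if that convention is written down.

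Three stronger readings are tempting and are not supported:

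- A reader might infer that the event disappears from the report. It does not; it leaves only the TEAE-based outputs.
- A reader might infer that counting Day 1 events before the first tablet biases the comparison. That is a conservative convention applied alike to all arms, and it matches the SAP's own default for unknown timing.
- A reader might size the loss by applying the Part A pruritus rate at 200 mg QD (3 of 5, 60%) to some share of patients with screening itch. No document gives that share. The 60% is the incidence of any pruritus, not the chance that existing itch worsens. Both Part B active arms also start at 100 mg QD.

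**Conclusion.** Wrong as written, with a limited consequence. The programmed rule does not implement the definition stated in the sentence before it or in the protocol, and SAP Section 5 does not declare the difference. The misclassification follows from the text for any AE that starts before the first dose, worsens after it and is kept on one record. It rests on one assumption that the documents leave open: that sites do not open a new, later-dated record for such worsening.

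The size is unknown. It is probably small, because several conditions must hold together for the same event. The direction described above also depends on the drug aggravating existing symptoms, which these passages do not quantify. Part B symptoms, pruritus above all, are the most exposed; the liver tests are largely protected by their shift tables. The Day 1 convention need not change.

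**What to change.** Extend the programmatic sentence in SAP 3.7.1 so that a TEAE is an AE with a start date on or after the first dose, or with a start date before the first dose and an increase in severity grade on or after it. In addition or instead, state in the SAP and the eCRF guidance that such worsening is entered as a new AE record dated at the worsening. The second option is needed if the eCRF keeps a single grade per record, because the program could not then see an increase; the documents do not say how grade is stored. If both are adopted, make sure that one worsening is not counted as two events.

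List all AEs with onset between consent and Day 1 and review them before database lock. SAP 4.2 includes adverse events in the first-step Part B analysis, so the review belongs before the first of the two locks.

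The cost is one SAP sentence, one line of eCRF guidance and one listing review. No design feature or efficacy analysis is affected.

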2.2 Secondary Objectives

The secondary objectives are the following:

- To explore the PK of EYP001a
- To evaluate PD effects of EYP001a on bile acid-related markers as appropriate
- To assess the effects of EYP001a on lipid and metabolic profiles
- To assess the safety of EYP001a with statin coadministration
- To assess the effects of EYP001a on noninvasive biomarkers of liver fibrosis and inflammation

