5.6.2 Restricted Medications and/or Procedures

Patients receiving statin therapy (rosuvastatin, atorvastatin, simvastatin, pravastatin, fluvastatin, or lovastatin are the only allowable statins) need to be on stable therapy for at least 90 days prior to the first administration of study drug. If LDL-C increases >10 mg/dL at Week 2, the statin dose may be increased and titrated up at the following visit if the LDL-C remains 5% above the baseline value.

For patients without statin therapy at baseline, if LDL-C increases $\geq 25\%$ from Day 1 to Day 14, rosuvastatin 20 mg QD will be introduced and titrated up to 40 mg QD at the following visit if LDL-C remains 5% above the baseline value.

Patients receiving other lipid-lowering treatments need to be on stable therapy for at least 90 days prior to the first study drug administration and must agree to remain on a stable regimen for their entire participation in the study. Patients with T2DM should be on a stable dose of antidiabetic medication for at least 90 days prior to screening and must agree to remain on a stable regimen for their entire participation in the study.

Close monitoring is required for comedication agents that are substrates for CYP2C8 or CYP2C9.

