9.8 Clinical Laboratory Evaluations

Clinical safety laboratory parameters will be measured or calculated at study visits specified in [Appendix A](#). Profiles for hematology, coagulation, serum chemistry, lipid and metabolic parameters, and urinalysis will be evaluated from samples collected after ≥ 6 hours of fasting (nothing by mouth except water). Further analysis of urine sediment or urine microscopy will be performed when there are any abnormalities on any of the following 3 dipstick results: leukocyte esterase, blood, or nitrite, and if judged clinically significant by the Investigator. See [Appendix B](#) for a complete list of laboratory analytes.

For women of childbearing potential, a serum hCG test will be performed at screening and the EOS and ET Visits. Urine hCG testing will be performed at visits specified in Appendix A. If a urine hCG test is positive, a serum hCG test will be performed.

Follicle-stimulating hormone level will be measured at screening to confirm postmenopausal state in women ≤ 55 years of age.

Anti-HBV, anti-HCV, and anti-HIV will be assessed at screening, and HCV RNA will be reflexively tested. Samples will be collected for central laboratory analysis except if viral serology data is already available in patient's medical history/records and obtained within 90 days prior to screening.

Plasma from blood samples obtained at screening and at study visits specified in Appendix A, including EOS and ET Visits, will be stored for protocol-related safety testing or exploratory analyses.

Blood sampling procedures, including information on blood volume, collection tubes, sample processing, storage, and shipping are provided in the Laboratory Manual.

The safety of statin coadministration will be assessed at study visits specified in Appendix A by monitoring CK levels.

Technical details on laboratory parameters (methods and commercial kit[s]) will be specified in the Laboratory Manual.

Additional laboratory testing may be required in response to adverse events and laboratory findings as described in the Clinical Safety Monitoring Plan ([Appendix E](#)). Laboratory abnormalities should be reported as an adverse event if any of the following is applicable:

- If an intervention is required as a result of the abnormality (such as a re-test being performed more than 1 time)
- If action taken with the study drug is required as a result of the abnormality

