2.2.2 Randomization and Blinding

This study follows a randomized, double-blind, placebo-controlled design. Patients in Part A will be randomized via the Interactive Response Technology (IRT) system to 1 of 4 parallel treatment groups on Day 1 in a 1:1:1:1 ratio. However, prerandomization will occur within the IRT system at least 7 days prior to randomization. Patients in Part B will be randomized via the IRT system to 1 of 3 parallel treatment groups on Day 1 in a 1:1:1 ratio. Prerandomization is not applicable in Part B.

Both EYP001a and placebo will be provided as tablets for oral administration and will be identical in appearance.

Prerandomization/randomization information will be concealed from the Investigators and the patients until the end of the study, with the exception of an emergency situation involving a patient that required unblinding of the treatment assignment.

Stratification

Randomization will be stratified by statin use (yes, no) and T2DM status (yes, no) in Part A, and by statin use (yes, no) and LFC (stratification factor with 3 categories: LFC<16%, 16%≤LFC<22%, and 22%≤LFC) in Part B at screening. Randomization can occur after eligibility check on Day -3, at the earliest, and prior to dosing on Day 1 at the latest.

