3.1.4 Analysis Visits

Refer to SAP V1.0 for Part A analysis visits.

Part B

For LFC, cT1, LSM and CAP, analysis visits will be assigned according to the labelled visit. I.e. "Baseline" analysis visit will be sourced from the "Screening" visit, and "Week 12/ET" analysis visit will be sourced from the "Week 12" or "ET" visit. Note that the ET assessment will be performed only for patients on study drug for ≥4 weeks.

For all other efficacy assessments with regular scheduled visits, analysis visits will be assigned according to the labelled visit. In addition to maximize the data available for assessments with regular scheduled visits, where possible, results from ET and unscheduled visits will be allocated to a post-baseline scheduled visit according to the following rules and visit windows

described in the table below (defined as the halfway point between the target visit days). If a valid value exists for the scheduled visit to which the ET/unscheduled visit has been allocated then the value from the scheduled visit will be used in the analysis, otherwise the values from the ET/unscheduled visits will be used in the analysis for the particular scheduled visit. If there is more than one assessment within a visit window, then the analysis visit will be assigned by the following priorities:

1. Use the assessment from the visit with the matching visit label.
2. Use the visit closest to the target visit day; in the case of ties, use the earlier visit.

Analysis Visit and Target Analysis Day	Visit Windows (Analysis Days)		
	Group I	Group II	Group III
Baseline	See Section 3.1.3		
Day 14 (Week 2)	2 – 21	2 – 21	
Day 28 (Week 4)	22 – 35	22 – 42	2 – 42
Day 42 (Week 6)	36 – 49		
Day 56 (Week 8)	50 – 61	43 – 70	43 – 77
Day 70 (Week 10)	62 – 77		
Day 84 (Week 12)	78 – 91	71 – 91	
Day 98 (Week 14) EOS FUP	92+	92+	92+
Group I: ALT, AST, AST/ALT Ratio, ALP, Total Bilirubin, Gamma-glutamyltransferase (GGT)			
Group II: hs-CRP, CK, BMI, Waist Circumference, Body Weight, Waist to Height Ratio, Waist to Hip Ratio, and lipids and metabolic profile			
Group III: HbA1c and all other biomarkers of liver fibrosis and inflammation			

Note that parameters that are considered both efficacy and safety (ALT, AST, CK) will use analysis visit windowing for both the efficacy and safety summaries and analyses for Part A and Part B.

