The number and percentage of patients with TEAEs will be summarized by reported maximum severity within each MedDRA preferred term within system organ class and by treatment group.

A further summary table for TEAEs by preferred term and system organ class will be provided for patients in the Safety Population who were taking a statin; a separate summary table will be provided for patients in the Safety Population who were not taking a statin. Patients who were and were not taking a statin will be identified from the appropriate stratification variable.

Detailed listings will be provided for all AEs. Separate listings will also be provided for AEs of Special Interest, SAEs, TEAEs leading to early discontinuation, TEAEs leading to temporary discontinuation of study drug and TEAEs leading to dose reduction.

For both Part A and Part B, an additional summary of derived pruritus TEAEs will be provided for the following categories:

- Grade 1 (mild or localized), defined as (severity grade 1 and (flagged as pruritus AESI on the eCRF or preferred term="Pruritus generalised")) or preferred term = "Pruritus"
- Grade 2 (widespread and intermittent), defined as severity grade 2 and preferred term = "Pruritus generalised"
- Grade 3 (widespread and constant), defined as severity grade 3 and preferred term = "Pruritus generalised"

3.7.2 *Pruritus Assessments*

Part A

The pruritus visual analog scale (VAS) and 5-D (degree, duration, direction, disability and distribution) itch scale will be assessed at Days 1, 7, 14, 21, 28, 56, 84 and 98 and also at the ET Visit.

Descriptive statistics for the pruritus VAS and 5-D itch scale will be presented for baseline values and for values and the change from baseline at each post-baseline visit.

Part B

In Part B, pruritus will be reported as any other AE. If a patient reports pruritus, the visual analog scale and the 5-D questionnaire (degree, duration, direction, disability, and distribution) itch scale will be administered. Results will be listed.

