3.7.3 Clinical Laboratory Tests

Serum chemistry, hematology, coagulation, lipid and metabolic profile parameters and urinalysis will be collected at the Screening Visit, Days 1, 7, 14, 21, 28, 56, 84, 98, and at the ET Visit (Part A) and at the Screening Visit, Days 1, 14, 28, 42 (ALT, AST, ALP, GGT, and total bilirubin only), 56, 70 (ALT, AST, ALP, GGT, and total bilirubin only), 84, 98, and at the ET Visit (Part B).

See Protocol Appendix B for analytes in the serum chemistry panel, additional chemistry parameters, hematology, coagulation, lipid and metabolic profile, and urinalysis.

The serum chemistry and additional chemistry parameters will be summarized and listed together.

Descriptive statistics of each safety laboratory parameter will be presented for baseline values and for values and the change from baseline at each post-baseline visit.

An additional summary table will be presented for CK over time for the patients in Safety Population who were taking a statin.

Values outside the normal range will be categorized as H (high, i.e. above the normal range) or L (low, i.e. below the normal range) based on the central laboratory's normal reference range. The number and percentage of patients with values outside the normal range will be summarized by parameter for each post-baseline visit.

Shift tables will also be presented for baseline vs. maximum post-baseline values and baseline vs. minimum post-baseline values for ALT, AST, Total Bilirubin and ALP. The shift tables for ALT and AST will include the following categories:

- < lower limit of normal (LLN) or Normal;
- > upper limit of normal (ULN) to $\leq 2 \times$ ULN;
- $> 2 \times$ ULN $\leq 5 \times$ ULN;
- $> 5 \times$ ULN to $\leq 8 \times$ ULN;
- $> 8 \times$ ULN.

The shift tables for Total Bilirubin and ALP will include the following categories:

- < LLN or Normal;
- > ULN to $\leq 1.5 \times$ ULN;
- $> 1.5 \times$ ULN to $\leq 2 \times$ ULN;
- $> 2 \times$ ULN.

ALT, AST, and Total Bilirubin will be assessed using the National Cancer Institute Common Terminology Criteria for Adverse Events (CTCAE). Shift tables will be presented for baseline vs. maximum post-baseline grades. The following categories are based on CTCAE Version 5.0 grading system:

Criteria	Grade 1	Grade 2	Grade 3	Grade 4

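### TEAE tables by statin use follow the screening stratum, so events after an on-study statin start are filed under no statin

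*SAP*

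**What the plan says.** Protocol 2.2 lists as a secondary objective: "To assess the safety of EYP001a with statin coadministration". Two sets of outputs serve it.

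- **TEAEs.** SAP 3.7.1 plans one TEAE table for Safety Population patients on a statin, and "a separate summary table will be provided for patients in the Safety Population who were not taking a statin". Membership is settled in the next sentence: "Patients who were and were not taking a statin will be identified from the appropriate stratification variable".
- **CK.** Protocol 9.8 states: "The safety of statin coadministration will be assessed at study visits specified in Appendix A by monitoring CK levels". SAP 3.7.3 responds: "An additional summary table will be presented for CK over time for the patients in Safety Population who were taking a statin". It does not say how those patients are identified.

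The stratum is a screening value. SAP 2.2.2 describes stratification by statin use and LFC category "in Part B at screening. Randomization can occur after eligibility check on Day -3, at the earliest, and prior to dosing on Day 1", so it is fixed before the first dose. SAP 3.3.4 keeps the value used at randomization even where it proves wrong, and only flags the error in listings.

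Statin use can change after that. Under Protocol 5.6.2, when a baseline non-user shows an LDL-C rise of 25% or more by Day 14, "rosuvastatin 20 mg QD will be introduced and titrated up to 40 mg QD at the following visit", the second step depending on LDL-C still being 5% above baseline. The rule is not restricted by arm.

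**The concern.** A patient who enters without a statin and starts one after Day 14 takes study drug and statin together for most of the treatment period. SAP 3.7.1 keeps that patient in the not-taking table throughout and never in the taking table. Events before the start are labelled correctly; events after it are not.

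Starters are informative for this objective. Patients on a statin at entry must have been stable on it for at least 90 days (Protocol 5.6.2) and are excluded if CK is above ULN, whereas other patients are excluded only above 3 x ULN (Protocol 4.3, criterion 20e). Starters are newly exposed to a statin while on study drug, and entered under the wider CK limit. A reader of the not-taking table would naturally take its events as arising without a statin.

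**Working it through.** The plan states no figure on this point, so there is none to reproduce. The check is first of text, then of size.

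**Text**

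1. Statin status in the TEAE tables is the stratification variable (SAP 3.7.1), which is the screening value (SAP 2.2.2) and is not updated (SAP 3.3.4).
2. A screening non-user can become a statin user on study (Protocol 5.6.2).
3. From 1 and 2, TEAEs after the start fall in the not-taking table.
4. SAP 3.3.6 counts any medication taken at the same time as or after the first dose as concomitant, and summarizes and lists statin use on that basis. The same starter is thus a concomitant statin user in 3.3.6 and a non-user in 3.7.1.
5. Nothing in SAP 3.3.6, 3.7 or 5 reclassifies starters or ties TEAEs to statin dates.
6. SAP 3.7.3 uses nearly the same phrase as 3.7.1. If the stratum rule applies, starters are left out of the CK table. If actual use applies, the visit from which they enter is not stated.

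**Size per starter, Part B**

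Inputs: 84 treatment days; trigger read at Day 14; next visit with a lipid panel at Day 28 (Protocol Table 8). Assumptions: the statin starts between those two visits and treatment runs to Day 84.

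- Earliest start: (84 - 14)/84 = 70/84 = 83% of treatment days follow the start.
- Latest start: (84 - 28)/84 = 56/84 = 67%.

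The upper figure is a limit, since the Day 14 laboratory result must be known first.

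SAP 3.1.4 places CK in the second window group ("Group II: hs-CRP, CK, BMI, Waist Circumference, Body Weight, Waist to Height Ratio, Waist to Hip Ratio, and lipids and metabolic profile"), and Protocol Table 8 limits Days 42 and 70 to liver tests. On-treatment CK visits are therefore Days 14, 28, 56 and 84.

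- Start before Day 28: Days 28, 56 and 84 follow, 3/4 = 75%.
- Start at Day 28: Days 56 and 84 follow, 2/4 = 50%.

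**Patients who could start, Part B**

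The documents give no start rate. Protocol 1.2.2 reports more than 50% on stable statin therapy, without saying clearly in which study. I assume 50% to 70% statin use at screening; the 70% has no source in the documents.

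- Non-users per arm of 30: 30 x (1 - 0.70) = 9 to 30 x (1 - 0.50) = 15.
- Non-users among the 26 per arm expected to complete: 7.8 to 13.
- For each 10% of non-users who start: 0.9 to 1.5 patients per arm, or 2.7 to 4.5 over three arms.
- Share of ever-users that a stratum-based CK table would miss, for each arm at that 10%: 0.9/(21 + 0.9) = 4% to 1.5/(15 + 1.5) = 9%.

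**The case against.** The strongest defence is that the stratum is the right grouping for comparing arms. It is fixed before treatment, so arms remain comparable within each table. Actual exposure is decided after randomization by an LDL-C change that study drug may itself influence (Protocol 1.2.3). The rule is also stated openly beside the table description. This stands, and it is why the two tables should be kept. It does not justify calling the groups taking and not taking.

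Second, other outputs cover much of the ground. Protocol 10.2.4.1 assesses statin coadministration by the difference in TEAE frequency between treatment groups, which does not use statin status. CK and muscle-related events are summarized by arm for all patients (SAP 3.7.1, 3.7.3), statin use and AEs are listed, and muscular events are adjudicated with a statin-specific index (Protocol Appendix E). No event is lost and cases can be reconstructed. This also stands and limits the harm, but a listing is a weak substitute for a summary on a stated objective.

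Third, a reader might infer that the CK table has no definition at all. That goes too far: it repeats the 3.7.1 phrase within the same SAP section, so the stratum rule most likely carries over. The gap is mainly a missing cross-reference, and the separate programming specifications (SAP 6) may settle it.

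Fourth, an exposure summary will have few patients per cell. True; a full split before and after the start by arm and preferred term is optional.

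**Conclusion.** The point holds as a labelling and completeness defect in descriptive safety tables. Followed exactly, SAP 3.7.1 files starters' later TEAEs under a label that is untrue for them, and no planned summary shows TEAEs by actual statin exposure. On the likely reading, the CK table omits starters.

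Per Part B starter, 67% to 83% of treatment days and 2 to 3 of 4 on-treatment CK visits are affected, assuming completion and a start between Days 14 and 28. How many starters there will be is unknown, so the total effect cannot be stated. Part A is not sized here.

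Two stronger readings are not supported. A reader might infer that the between-arm safety comparison is biased; it does not depend on statin status, and the within-stratum comparisons stay valid as well. A reader might also infer that misfiling rises with dose. In Part B both active arms take 100 mg QD up to the Day 14 trigger (Protocol 5.1, Table 2), so no dose-related difference in starts between them is expected. Active and placebo arms could differ, but the documents give no rate.

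No efficacy result is touched. The change is worth making because it is cheap and serves a stated objective.

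**What to change.** 1. Keep both stratum-based TEAE tables and title them *statin use at screening: yes* and *no*.
2. Add one TEAE summary by treatment group and actual statin exposure from concomitant-medication dates: user at screening; on-study starter, with events after the start shown; never user. Give at least overall and muscle-related TEAEs. Label it descriptive and non-randomized.
3. State in SAP 3.7.3 which definition the CK table uses, and show on-study starters separately from their start date, because their entry CK limit differed.
4. Tabulate on-study statin starts by arm.

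No change to the statin rule itself is proposed.

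Cost: a retitle, a definition and a few descriptive tables. Protocol 5.6.3 already requires concomitant medications and their dosing changes in the eCRF, so no new data are needed. The drawback is small cells and grouping on a post-randomization event, so the added summary supports description only.
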